4.1.1 Risk adjustment using aggregate predicted mortality

Briefly, sensitivity analyses will use iCOMPARE program-level risk-adjusted data on 30-day mortality by aggregating the patient-level risks derived from our fitted models. We will compute each patient's predicted 30-day mortality in the pre-trial period as we did in previous work (9-11). We will then average the predicted 30-day mortality for all patients in a program in the pre-trial period to obtain program i 's expected 30-day mortality rate in the pre-trial period, call it RA_{pi} , and average the predicted 30-day mortality for all patients in a program in the trial period to obtain what program i 's expected 30-day mortality rate would have been had these same patients been treated in the pre-trial period, which we call RA_{ti} . Then we update model A1 (at the program level) to include a term for the difference ($RA_{ti} - RA_{pi}$) so that the coefficient on treatment assignment is our estimate of being assigned to treatment versus not being assigned on the change in the outcome (e.g., mortality rate), adjusting for any changes in the risks of the patients at the program.

The model (Model B) is:

$$Y_i = \beta_0 + \beta_1 x_{1i} + \beta_2 x_{2i} + \varepsilon_i, \quad i = 1, \dots, n_p, \text{ where}$$

Y_i

= Mean outcome measure in IM program i (e.g., Trial year 30-day mortality - Pre-trial 30-day mortality)

$x_{1i} = 1$ if the i th IM program is in **Flex**, 0 if the i th IM program is in **Curr**

$x_{2i} = (RA_{ti} - RA_{pi})$

β_0 = Intercept for the IM programs

ε_i = i. i. d. random Gaussian errors with mean 0 and variance σ^2

n_p = Number of clusters (IM programs)

The adjusted non-inferiority tests will be t-tests based using the same non-inferiority margin (1%) and the estimates and standard errors for β_1 from the regression models. The model estimates, 95% CIs, and p-values will be derived using Stata, R or SAS.

4.1.2 Risk adjustment using aggregate predicted mortality

A key set of secondary analysis will use multivariable risk adjustment modeling used by our DCC group in past analyses of Medicare data for non-randomized comparisons of resident duty hour policy changes (9, 10). These secondary analyses related to our primary aim of whether 30-day mortality under the Flex duty hour schedule is not inferior to 30-day mortality under the **Curr** duty hour schedule and will use multivariable program-level and patient-level risk adjusted analyses appropriate for multiple time series research designs like iCOMPARE. The model will be a multivariate risk adjusted logistic models for patient level 30-day mortality in relation to **Flex** vs. **Curr**, year, **Flex** vs. **Curr** by year interaction, and program-level and patient-level risk factors for mortality. These designs, also known as “Difference-in-Differences” designs, reduce potential biases from unmeasured variables. The multiple time series research design compares each program with itself (comparison of an outcome in the year before the duty hour intervention versus the outcome in the year of the duty hour intervention), making adjustments for observed differences in patient risk factors and adjustments for changes in outcomes over time (trends) that were common to all programs. This design prevents bias from 3 possible sources. First, a difference between programs that is stable over time cannot be mistaken for an effect of the trial, because each program is compared with itself. Because of this, program indicators for fixed effects are used in the logistic model. Second, changes over time that affect all programs similarly (e.g., technological improvements) cannot be mistaken for an effect of the trial. Because of this, year indicators are used in the logistic model. Third, if the mix of patients is changing in different ways at different programs, and if these changes are accurately reflected in measured risk factors, this cannot be mistaken for an effect of the duty hour schedule because the logistic model adjusts for these measured risk factors. For example, this approach addresses concern about local differences in, for example, influenza rates that may affect the distribution of patient diagnoses or outcomes year-to-year inside the same hospital. However, we will be including the principal diagnosis and secondary diagnoses in the Difference-in-Differences model, so the distribution of diagnoses will be accounted for in the adjustment model, eliminating concerns about this type of potential bias.

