5.3. Patients

Our study population for evaluation of patient safety and costs will be Medicare fee for service (FFS) beneficiaries at least age 65.5 years at hospital admission and admitted to one of the acute care hospitals affiliated with the randomized IM programs and at which the IM program implements the randomly assigned duty hour schedule between July 1, 2015 and June 30, 2016 and with any of the eligible principal diagnoses (see Table 15.5). These diagnoses apply to the majority of patients on a typical medical service and account for most of the deaths and other safety indicators. [26] While patients who are not Medicare beneficiaries are also cared for by trainees, 67.3% of patients on the medical services are Medicare beneficiaries and 72.2% of the mortality in medical admissions is in Medicare beneficiaries.[27, 28] The analyses are limited to FFS beneficiaries because CMS claims data are available for Medicare FFS patients only. All FFS Medicare patients will have complete, linked data: inpatient (Medicare Part A), outpatient, physician (Medicare Part B), and associated denominator files. Patients will be included if they were not enrolled in a managed care program six months before admission and one month post

discharge. The minimum age is 65.5 years and FFS status in the 6 months prior to admission is required so that claims are available for 6 months prior to the qualifying admission. The diagnoses were chosen to reflect the vast majority of patients on the typical IM service. Examining all patients, rather than just Medicare aged FFS patients, would be ideal but is not feasible because 30-day mortality, as well as the secondary outcomes, require 'linkable' data to events occurring outside the hospital, something not practical to obtain outside the Medicare system (i.e., it would be impractical to consent patients to be able to see their data, or to rely on numerous insurance companies or various state databases due to the scale of this trial). No patients will be excluded based on gender or race/ethnicity. We expect very little change in year to year demographic and clinical characteristics of the patients admitted to each hospital, as we observed in previous studies [9, 29].

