We will address the change in ICD codes as follows. We will use the official crosswalk between the two coding systems and ensure that the principal diagnosis codes for the index admissions include all the possible codes identified in the crosswalk in both systems. Secondly we will have a separate dataset in which we will experiment and test the validity of the crosswalk, which is not part of the safety outcomes and cost analysis. This dataset will serve as the lab for the investigators to define the medical admissions in the ICD10 system in a way that is consistent with the ICD9. The lab data set will comprise patients admitted to hospitals affiliated with the remaining 137 eligible IM programs that did not elect to participate in iCOMPARE. This way we ensure that our experimental data are very similar to the data obtained for the programs participating in iCOMPARE. After we are satisfied with the validity of the crosswalk, we apply it to claims at hospitals affiliated with the randomized programs. It is helpful that the list of possible complications in medical admissions is limited.

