4.1 Patient safety hypothesis H1a – 30-day mortality

The primary outcome will be the difference between the pre-trial year and trial year 30-day mortality rates as described above.

The model (model A1) is:

$$Y_i = \gamma + \beta_1 x_i + \varepsilon_i, \quad i = 1, \dots, n_p \text{ where}$$

Y_i = Outcome measure in IM program i = Trial year rate - Pre-trial year rate,

γ = the intercept in the reference group (**Curr**),

β_1 = the difference in intercepts between **Flex** and **Curr**,

$x_i = 1$ if the i th IM program is in **Flex**, 0 if the i th IM program is in **Curr**

ε_i = i.i.d. random Gaussian errors with mean 0 and variance σ^2

n_p = Number of clusters (IM programs)

We will test β_1 (or $\beta_1 - nim$, where nim is the non-inferiority margin) ≤ 0 ; β_1 is the expected difference in outcome: **Flex** vs. **Curr**. All randomized programs will be included in this model and we expect no missing data.

The primary outcome measure for this cluster-randomized trial is the difference in 30-day mortality rates during the trial year versus the prior, which is 58 rate differences, 1 per randomized program, with a two-sample t-test for non-inferior patient mortality (difference no greater than 1%), comparing the **Flex** vs. **Curr** schedules. This approach permits the use of a simple model (two-sample non-inferiority t-test) for the set of at least $N=29$ pairs of trial year vs. pre-trial year differences in each group (**Curr** vs. **Flex**) in annual 30-day mortality rates following the paradigm elaborated by Hayes and Moulton (8) in their book on cluster randomized trials (CRTs). The model obviates the need for complex risk adjustment models, since it adjusts for secular trends in 30-day mortality that were common to all hospitals (e.g., severe flu season, technological improvements), as well as removing variation due to IM program population risk profiles (e.g., geography, patient characteristics) that are likely to cancel out by comparing successive years within IM program.

While these rate differences should adjust for most program to program differences in patient and institutional mix, we will also perform an important series of sensitivity analyses using risk-adjustment modeling methods that we developed (9) and which we will apply to the iCOMPARE data to confirm the findings of the primary analysis or to add a risk-adjustment caution to the statements of findings.

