4.2 Other patient safety hypotheses – H1b-H1e

The following outcomes are the remaining outcomes for the patient safety and cost hypotheses:

- a) Patient safety and costs hypothesis H1b:
 - Measure: 7-day and 30-day hospital readmission rates
 - Non-inferiority margin: 1%
- b) Patient safety and costs hypothesis H1c:
 - Measure: complications rates, defined by selected AHRQ Patient Safety Indicators
 - Non-inferiority margin: 1%
- c) Patient safety and costs hypothesis H1d:
 - Measure: The rate of prolonged length of hospital stay defined as a stay that exceeds the Hollander-Proschan point or that length of stay for a given condition at which the discharge rate begins to decline (1)
 - Non-inferiority margin: 1%
- d) Patient safety and costs hypothesis H1e:
 - Measure: Overall resources utilized and Medicare payments for patient care
 - Non-inferiority margin: 1%

Analyses for H1b-e will use the same approach described for model A1 with either linear, logistic, or Poisson models depending on whether the outcome measure is a rate, measured/ordered, a proportion, or a count.

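### The SAP 4.1.2 mortality model adjusts for secondary diagnoses without limiting them to conditions present by admission, so a key secondary analysis could adjust away part of any harm from Flex

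*Combined protocol and SAP*

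**What the plan says.** The primary analysis of H1a (SAP 4.1, model A1) compares program-level changes in 30-day mortality by arm, with no patient covariates. Of the rate-difference approach the SAP says: "The model obviates the need for complex risk adjustment models". It then adds risk-adjusted sensitivity analyses, whose purpose is "to confirm the findings of the primary analysis or to add a risk-adjustment caution to the statements of findings".

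SAP 4.1.2 describes one of these in stronger terms: "A key set of secondary analysis will use multivariable risk adjustment modeling used by our DCC group in past analyses of Medicare data". It is a patient-level logistic model with arm, year, their interaction, program indicators and risk factors. On the risk factors it says: "we will be including the principal diagnosis and secondary diagnoses in the Difference-in-Differences model". The stated reason is that local events such as influenza may change the mix of diagnoses within a hospital from one year to the next.

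Model B (SAP 4.1.1) adjusts for the change in each program's average predicted mortality and keeps the 1% margin. The hierarchical model (SAP 4.1.3) includes patient-level risk factors. Neither section lists its patient-level predictors.

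For H1c, SAP 4.2 gives "Measure: complications rates, defined by selected AHRQ Patient Safety Indicators", also taken from Medicare claims and also with a 1% margin. On look-back data, Protocol 5.3 says: "FFS status in the 6 months prior to admission is required so that claims are available for 6 months prior to the qualifying admission". No passage ties those earlier claims to the secondary diagnoses in SAP 4.1.2.

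**The concern.** A risk adjuster should describe the patient before the assigned schedule can act. The SAP is alert to one error, a change in patient mix being taken for a schedule effect. It has no safeguard against the reverse, a schedule effect being taken for patient mix.

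If diagnoses first coded during the qualifying stay are allowed in, one event can be an outcome under H1c and a case-mix variable under H1a. Suppose Flex led to more complications and some of those patients died. The adjusted model would attribute those deaths to sicker patients, and the Flex-by-year term would shrink toward no difference. In a non-inferiority safety trial that is the reassuring direction. What is at stake is how far the adjusted analyses can be trusted when they are cited in support of the primary result.

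**Working it through.** **Does the text admit post-admission codes?** SAP 4.1.2 pairs secondary diagnoses with the principal diagnosis, which in Protocol 5.3 belongs to the qualifying admission. Its influenza rationale concerns what patients are admitted with in a given year, which claims from the preceding 6 months would mostly miss. Both point to current-stay codes. No present-on-admission rule, look-back restriction or exclusion of complication codes appears in the protocol or SAP. Post-admission codes are therefore not shown to be included, but nothing keeps them out.

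**The plan's own figure.** Inputs from SAP 3: margin 1 point, true difference 0, SD 1.5 points, 29 programs per arm, one-sided alpha 0.05.

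- SE = 1.5 × √(1/29 + 1/29) = 0.394 points
- df = 29 + 29 − 2 = 56; critical t = 1.673
- Noncentrality = (1 − 0)/0.394 = 2.54
- Power from the noncentral t = 0.8059, as stated. The same steps with 40 per arm give 0.9050, also as stated.

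**Illustration for Model B.** SAP 4.1.1 specifies a t-test with the 1% margin, so the same formula applies if its predictors include current-stay codes. Assume a true harm of exactly 1 point, of which adjustment removes a fraction f, and keep the SD at 1.5 points (assumed unchanged by adjustment). The harm left is (1 − f) points, so noncentrality = [1 − (1 − f)]/0.394 = f/0.394.

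| f (assumed) | Noncentrality | Chance of a non-inferior adjusted result |
|---|---|---|
| 0 | 0 | 5.0% |
| 0.25 | 0.63 | 15.4% |
| 0.50 | 1.27 | 34.8% |
| 0.75 | 1.90 | 59.3% |
| 1 | 2.54 | 80.6% |

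For the 63 programs actually randomized (Protocol 6.1), with an assumed 31/32 split, the chances are 5.0%, 16.1%, 36.8%, 62.4% and 83.4%. The logistic model in SAP 4.1.2 has no stated margin or SD, so these probabilities do not transfer to it directly.

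**How much harm could run through complications?** The documents give baseline mortality of 11% but no complication rate and no mortality excess per complication. Assume a base complication rate of 5 to 10% and an excess mortality of 10 to 30 points per complication.

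- If Flex raises complications by 1 point (the H1c margin), added mortality = 0.01 × 10 to 30 points = 0.1 to 0.3 points. The unadjusted odds ratio runs from (0.111/0.889)/(0.11/0.89) = 1.010 to (0.113/0.887)/(0.11/0.89) = 1.031. With the complication as a covariate it is 1.000.
- For a full 1-point harm acting only this way, complications must rise by 1/0.30 = 3.3 points to 1/0.10 = 10 points. The unadjusted odds ratio is (0.12/0.88)/(0.11/0.89) = 1.103; adjusted, it is 1.000.

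The adjusted value of 1.000 follows from routing all the harm through the coded complication. Harm acting by other routes is not removed in this way.

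**The case against.** The strongest reply is that SAP 4.1.2 never names the claim from which secondary diagnoses are taken. Protocol 9.2 collects encounters for at least 6 months before admission and plans risk-adjustment models built on baseline claims. A look-back definition is compatible with the text, and the earlier published analyses whose methods the SAP adopts may handle complications explicitly. This stands in part. It rules out saying that the model certainly contains in-hospital complications. It does not close the gap, because the plan itself sets no limit and its wording leans toward current-stay codes.

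Two stronger inferences are tempting and fail. A reader might infer that the trial's chance of wrongly declaring non-inferiority rises above 5%. It does not: that decision rests on A1, which has no patient covariates. A reader might also infer that an adjusted result could override an adverse primary result. SAP 4.1 lets these analyses only confirm the finding or attach a caution to it.

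It is also fair to say that a complication rise large enough to hide a full 1-point harm, 3.3 points or more under the assumed rates, is over three times the H1c margin. H1c, reported separately, should then show it. That limits the damage but does not make the adjusted mortality estimate correct.

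**Conclusion.** The concern holds as a gap in covariate definition with a known direction of bias. Followed literally, SAP 4.1.2 can adjust for events that H1c treats as consequences of the schedule. The part of any Flex mortality harm acting through them would be lost from a key secondary analysis. SAP 4.1.1 and 4.1.3 share the problem only if their unlisted predictors use such codes. The primary test, its error rate and its power are unchanged.

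The size cannot be fixed from the documents. The Model B probabilities rest on an assumed harm equal to the margin, an assumed removed fraction and an unchanged SD. Complete masking requires all harm to act through coded complications, which nothing in the documents supports. A complication rise of only 1 point would hide a small fraction of the margin under the assumed rates.

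**What to change.** In SAP 4.1.1 to 4.1.3:

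1. Limit patient-level risk adjusters to demographics, the qualifying principal diagnosis and comorbidities found in claims from the 6 months before admission.
2. Use secondary diagnoses from the qualifying claim only where they can be shown to be present on admission. The documents do not mention such a marker, so first check whether the claims files carry it.
3. Exclude secondary diagnosis codes that define an H1c complication in the same stay. Do not extend this to principal diagnoses: Protocol 15.5 lists conditions such as septicemia, acute kidney failure and pulmonary embolism as qualifying diagnoses, and the selected H1c indicators are not listed.
4. Report the model without index-stay secondary diagnoses alongside any version that uses them.

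The cost is SAP wording and covariate programming. The look-back claims are already within the data the trial plans to obtain (SAP 2, Protocol 9.2), although the schedule in Protocol 15.7 has some requests still to come in Fall 2016 and Fall 2017. The downside is that chronic conditions coded only on the qualifying claim would be lost, so the adjustment would explain somewhat less variation. Sample size and stated power do not change.

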
4.1.3 Hierarchical models

We will do another sensitivity analysis using hierarchical logistic regression models for patient-level 30-day mortality in relation to fixed training program-level and patient-level risk factors **Flex** vs. **Curr**, year (trial vs pre-trial), **Flex** vs. **Curr** by year interaction and random effects to account for within-program correlations consisting of programs, hospitals, and patients. Hierarchical models are a different approach to risk adjustment and adjustment for within cluster correlation. We summarized our approach above. The key issues with such models relate to assumptions about the random effects (we assume Gaussian deviations in effects) and which effects are fixed, which are random, and which are both. These are difficult choices to make at the design phase.

However, hierarchical models do have appeal. For example, it is possible that there are things that affect a whole program or hospital in a specific year, e.g., a new program director is hired one year. The fixed

effects take account of program effects that are constant across all years of study, but not effects that are just present for one particular year. While we believe that single year effects will be rare and limited to a few hospitals, one approach would be to use robust standard errors that are clustered on training programs. This is the approach suggested by Angrist and Pischke (12) when there are at least 42 clusters, which is our setting. However, fitting a random effects model with random effects for program, hospital, attending, and patient would also be a way to account for these program*year effects, but probably harder to fit. Another issue relates to the few cases where one hospital has multiple programs in it so that there would be crossed random effects between program and hospital. In rare cases, a patient can be seen by two different programs at different times, this would also create crossed random effects. In principle, these configurations make the approach suggested above using robust standard errors that are clustered on program not fully valid as it would not take into account this crossing. Crossed random effect models are considerably harder to fit than nested random effect models, but it might be possible.

Despite, potential difficulties, we believe that hierarchical models will give us exploratory insights into our data and may help to understand effects or lack of effects arising from iCOMPARE.

4.1.4 Potential effect modification

Despite the sub-optimal power for comparisons of variability in non-inferiority of **Flex** versus **Curr** across subgroups of programs, we will explore the extent to which the effect of the **Flex** versus **Curr** schedule on the outcomes listed above differs in several subgroups of interest. We will compare the treatment effects in subgroups by testing for treatment (**Flex** vs. **Curr**) by subgroup interactions in the models described above. The pre-specified key subgroups of interest are 1) nonteaching versus teaching hospitals (2, 9), 2) resident to bed ratio (10) (categorized into tertiles), 3) percentage of inpatients (2) (categorized into tertiles), 4) geography (northeast, southeast, midwest, southwest, west). Other subgroups of interest may be examined in response to journal reviews or other, as yet unstated, reasons.

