- Trainee education and process outcomes
 - Intern work intensity, ownership, and continuity measures (iCOMPARE surveys)
 - Intern time in direct patient care and other activities (Time and Motion Substudy)
 - Trainee satisfaction, burnout, and attitudes (iCOMPARE and ACGME surveys)
 - Intern knowledge (ACP ITE score)
 - Faculty satisfaction with training and teaching experience (ACGME survey)
 - Program director satisfaction and perceptions of training safety, teamwork and supervision (iCOMPARE and APDIM surveys)
- Intern sleep and alertness outcomes (Sleep and Alertness Substudy)
 - Sleep-wake times (wrist actigraphy)
 - Onset and offset times of sleep periods in past 24h (interview)
 - Perceived sleepiness (Karolinska Sleepiness Scale)
 - Behavioral alertness (psychomotor vigilance performance)

Sample size justification for mortality outcome

- Planned sample size: 58 graduate medical education training programs in Internal Medicine selected from ACGME list of candidate IM programs; the planned total number of hospitals across the training program clusters is 100+ (some programs span more than one hospital)
- Sample size determined to be adequate to test the hypothesis that 30-day mortality among Medicare beneficiaries in defined high risk DRGs (30-day mortality = 11%) in the intervention flexible schedule is not inferior to the corresponding mortality in the current 16 hour limit (control) schedule by a margin no greater than 1%
- Unit of analysis: IM training program
- Primary outcome measure: Difference (trial year vs. pre-trial year) in 1-year 30-day mortality
- Power: > 0.80
- Type I error (alpha): 0.05
- Primary analysis method: one-sided two-sample t-test for a noninferiority margin of 1%
- Software for sample size calculations: PASS 11

Recruitment goals

- 58 IM programs encompassing 100+ hospitals

Selection criteria for programs to be randomized

- Resident to bed ratio > 0.105 (excluded bottom 50% of hospitals by resident to bed ratio)
- Sufficient patient volume (excluded bottom 25% of hospitals by patient volume)
- Consent to participate
- Current ACGME accreditation

Consent issues

- ACGME has provided a waiver allowing programs to participate in COMPARE
- Programs: consent to randomization and obtain local IRB approval

- Hospitals: programs must provide evidence of buy in/consent of their hospitals
- Patients
 - They do not consent
 - They are not informed about the trial

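### SAP 4.1.4 tests effect modification with Flex-by-subgroup in every model, but in the patient-level mortality models the treatment effect is Flex-by-year, so the test there should be Flex-by-year-by-subgroup

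*Combined protocol and SAP*

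**What the plan says.** SAP 4.1.4 lists four pre-specified subgroup factors: teaching status, resident-to-bed ratio in tertiles, percentage of inpatients in tertiles, and five geographic regions. It concedes that power is limited. Its rule is: "We will compare the treatment effects in subgroups by testing for treatment (Flex vs. Curr) by subgroup interactions in the models described above".

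The models it points back to are of two kinds.

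- **Program-level change models.** Model A1 (SAP 4.1) has one row per program, and its outcome is "Trial year rate - Pre-trial year rate". Model B (SAP 4.1.1) has the same outcome and adds the change in predicted risk.
- **Patient-level models on stacked periods.** The logistic model of SAP 4.1.2 is specified "in relation to Flex vs. Curr, year, Flex vs. Curr by year interaction, and program-level and patient-level risk factors for mortality", and "program indicators for fixed effects are used in the logistic model". The SAP calls it a difference-in-differences design. The hierarchical logistic model of SAP 4.1.3 lists the arm contrast and then "year (trial vs pre-trial), Flex vs. Curr by year interaction and random effects to account for within-program correlations".

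Neither the SAP nor the protocol names a three-way interaction.

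**The concern.** In A1 and B the arm coefficient is the effect on change, so an arm-by-subgroup term measures effect modification. In 4.1.2 and 4.1.3 the arm contrast and its interaction with year are separate terms. The arm contrast covers both periods, including the one before the intervention. The interaction with year carries the treatment effect, so effect modification there is arm by year by subgroup.

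A programmer who follows 4.1.4 to the letter would fit a term that drops out of the fixed-effects model. In the hierarchical model the same term would answer a different question, namely whether the arms differ by subgroup on average over both periods. At stake is the reading of the subgroup results from what SAP 4.1.2 treats as a key secondary analysis and from the sensitivity analysis of 4.1.3. If the term is settled only once results are visible, the choice can be driven by the data.

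**Working it through.** **1. The plan's own figure.** The SAP states no power for subgroup tests. Its primary calculation (SAP 3) uses SD 0.015 for the program rate differences, margin 0.01 and one-sided alpha 0.05. The noncentrality is 0.01 / (0.015 x sqrt(2/n)).

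- n = 29 per arm: 2.539 on 56 df, power 0.8059.
- n = 40 per arm: 2.981 on 78 df, power 0.9050.

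Both match the SAP, so a change SD of 1.5 points is used below.

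**2. What each term estimates.** Let F be arm, S a binary subgroup and t year (0 pre-trial, 1 trial). Write the mean as

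a + bF + cS + dFS + t(e + fF + gS + hFS).

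Here d is the pre-trial arm-by-subgroup difference and h is the effect modification.

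- Change outcome (A1; B likewise, given the risk term): the mean is e + fF + gS + hFS, so the F x S coefficient is h. The rule is correct.
- Stacked periods, F x S without a three-way term, equal volumes in the two years: the coefficient is [d + (d + h)]/2 = d + h/2.

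Protocol 9.2 builds two baseline cohorts. If both were stacked with equal volumes, the coefficient would be (3d + h)/3 = d + h/3.

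**3. SAP 4.1.2: rank of the design.** Assignment is by program, so F x S for a program-level subgroup is the sum of the indicators of the Flex programs in that subgroup. With 58 programs, the base design is 58 indicators + year + Flex x year = 60 columns, rank 60.

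| Subgroup levels | Add Flex x subgroup: columns / rank | Add subgroup x year and Flex x year x subgroup: columns / rank |
|---|---|---|
| 2 | 61 / 60 | 62 / 62 |
| 3 | 62 / 60 | 64 / 64 |
| 5 | 64 / 60 | 68 / 68 |

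The stated term adds no rank; the three-way set is fully estimable. The argument does not depend on the number of programs, so it also holds for the 63 randomized (Protocol 6.1). If a modifier varies between hospitals of one program, Flex x modifier raises the rank from 61 to 62. It is then estimable, but it is again an arm difference averaged over both periods.

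**4. SAP 4.1.3: size of the dilution.** Assumptions, not in the documents: a balanced binary subgroup (cells 15, 14, 14, 15), program-year rates on a linear scale without covariates, a two-sided 5% test, and between-program SD (tau) of 1, 2 or 3 points.

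- k = sqrt(1/15 + 1/14 + 1/14 + 1/15) = 0.5255.
- Three-way SE = 1.5 x 0.5255 = 0.788 points.
- Yearly error variance = 1.5^2 / 2 = 1.125. Variance of a program's two-year mean = tau^2 + 1.125/2 = tau^2 + 0.5625.
- Two-way SE = sqrt(tau^2 + 0.5625) x 0.5255 = 0.657, 1.123 and 1.625 points.

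Power from the noncentral t with 54 df, taking d = 0:

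| True h | Three-way: mean, power | Two-way: mean, power at tau = 1, 2, 3 |
|---|---|---|
| 2.0 | 2.0, 70% | 1.0, 32% / 14% / 9% |
| 1.5 | 1.5, 46% | 0.75, 20% / 10% / 7% |

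Simulation with 2,000 runs per setting agrees. At h = 2 the two-way term averaged 1.0 point and rejected in 31% (tau = 1) to 14% (tau = 2) of runs; the three-way term averaged 2.0 points and rejected in about 70%.

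**5. Pre-trial imbalance.** With h = 0 and no systematic imbalance, the two-way test rejected in 4% to 5% of runs. With h = 0 and d held at 1 point, it rejected in 32% (tau = 1) to 14% (tau = 2), while the three-way test stayed at 4% to 6%.

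**The case against.** The best defense is that the sentence in 4.1.4 speaks of comparing treatment effects, and that 4.1.2 makes plain the effect is a difference-in-differences. On that reading, treatment by subgroup already means the Flex-by-year effect by subgroup. The SAP also describes its models loosely: it lists an arm main effect beside program indicators that absorb it. This reading is plausible and may be what the authors meant. But the parenthesis in 4.1.4 uses the same label that 4.1.2 and 4.1.3 give to the main effect, which they list apart from the interaction with year, and no three-way term is written anywhere. The rule as written still selects the wrong term.

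Other points stand and limit the concern.

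- Models A1 and B give a valid subgroup test in any case. A reader might infer that harm from Flex in a subgroup would usually be missed; the documents do not support that.
- A reader might infer that A1 and B cannot serve because the modifiers belong to hospitals. Protocol 15.3 does say "the planned total number of hospitals across the training program clusters is 100+ (some programs span more than one hospital". But 4.1.4 frames the question as variation between groups of programs, and only its first factor names hospitals.
- In 4.1.2 a dropped term is visible to the analyst and produces no false result.
- SAP 4.1.3 describes its own model as exploratory.
- Two planned factors are tertiles and one has five levels, and the real models are risk-adjusted logistic, so the power figures illustrate rather than predict.

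**Conclusion.** Wrong as written, with moderate consequence. For SAP 4.1.2 with a program-level subgroup, the stated term is not estimable; this is algebra and needs no assumption about variance or effect size. For 4.1.3, and for 4.1.2 with any modifier that varies within a program, the term estimates the pre-trial difference plus half the heterogeneity when the two periods have equal volume. The halving follows from the model. The power loss (70% down to between 32% and 9% at 2 points) rests on the assumed subgroup split, linear scale and between-program SD.

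Two stronger readings are tempting and should not be drawn. The primary analysis is not compromised, because Flex x subgroup is the right term in A1 and B. Nor is type I error inflated overall: randomization makes the expected pre-trial imbalance zero, and the two-way test held its level when no systematic imbalance was imposed. The harm is dilution, lost power, and bias conditional on the imbalance that happens to occur.

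**What to change.** In SAP 4.1.4, replace the single rule with: *In Models A1 and B effect modification is tested by Flex x subgroup; in the patient-level models of 4.1.2 and 4.1.3 it is tested by Flex x year x subgroup, with subgroup x year and all other estimable lower-order terms.*

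This costs one sentence in the SAP and one changed term in the code of two models. It needs no new data, and it should be settled before trial-year mortality is examined.
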